6.4.2. Analysis of Exploratory Serum Lipid Profiles Endpoints

The observed values and the change from baseline and percent change from baseline in serum lipid profile endpoints, total cholesterol, LDL, HDL, VLDL, triglycerides and FFA, will be summarized descriptively by cohort/dose level and time point.

A similar mixed model repeated measures analysis as described previously will be performed for the change from baseline and percent change from baseline in serum lipid profile endpoints.

6.4.3. Analysis of Exploratory Amino-Acid Profile Endpoint

The observed values and the change from baseline in amino-acid profile will be summarized descriptively by cohort/dose level and time point.

6.4.4. Analysis of Exploratory Glucose Metabolism Parameter Endpoints

Fasting plasma glucose, glucose via YSI, insulin, c-peptide, HbA1c, fructosamine, and glycated albumin measurements and change from baseline will be summarized by dosage and visit. A similar mixed model repeated measures analysis as described previously will be performed for the change from baseline and percent change from baseline in each of these parameters.

Individual SMBG measurements of each time point, as the daily/weekly mean, the daily/weekly pre-meal mean and daily/weekly post-meal mean measurements will be presented in a listing. Subject SMBG of each time point, the daily/weekly mean of pre-meal and post-meal SMBG will be summarized by part/cohort/dose level as well as change from baseline. Mean SMBG (+/- SD) at each time point of baseline, Week 1 and Week 12 will be plotted.

6.4.5. Analysis of Exploratory Homeostatic Model Assessment Endpoints

Observed values and the change from baseline in HOMA endpoints such as, HOMA-IR and HOMA- β , will be summarized descriptively by cohort/dose level and time point.

A similar mixed model repeated measures analysis as described previously will be performed for the change from baseline in HOMA endpoints.

6.4.6. Analysis of Exploratory MRI Endpoints

Observed values and the change from baseline (absolute) and percent change from baseline (relative) in MRI endpoints such as of liver fat via MRI-PDFF and visceral fat volume, will be summarized descriptively by cohort/dose level and time point. **Note:** MRI-PDFF at Day 85 is only measured if the Day -1 or Baseline visit is $\geq 10\%$ liver fat.

A Wilcoxon Mann Whitney test will be performed to test the change from baseline and the percent change from baseline in MRI endpoints by treatment group. The p-value from the Wilcoxon Mann Whitney test will be presented. In addition, the estimate of the median and the exact 95% confidence limits estimated by the Hodges-Lehmann estimator will be presented.

In addition, an analysis of variance (ANOVA) model will be performed; the difference between each HM15136 dose group and placebo and its associated 95% confidence interval and p-value will be presented.

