MRI-PDFF test is used to assess absolute and % changes of liver fat. This test is performed prior to Day -1 for all eligible subjects (MRI may be performed while Screening calcitonin results are pending). This test should be conducted as close as possible to the Day 85 of the 12th week before the Day 85 PK sampling. However, on Day 85 of the MRI-PDFF measurement, the MRI-PDFF will only be conducted if the liver fat on Day -1 was equal to or greater than 10% (\geq 10%).

Per COVID-19 modification, If MRI/MRI-PDFF assessment is not possible during the stated time period, due to COVID- restrictions, MRI/MRI-PDFF may be performed at a later timepoint, but prior to the last visit possible, on Day 113. If MRI/MRI-PDFF assessment is not possible due to restricted access of MRI center under COVID-19 restrictions, the missing assessment will be documented in the CRFs (specific information will be captured that explains the basis of the missing data due to COVID-19). The missing assessment will be documented as a protocol deviation (with reason due to COVID-19 stated).

② MRI imaging

The MRI imaging will be used to assess changes in visceral fat volume, determined by absolute and relative percent changes. This test is performed prior to Day -1 for all eligible subjects (MRI may be performed while Screening calcitonin results are pending). This test should be conducted as close as possible to the Day 85 of the 12th week before the Day 85 PK sampling.

Per COVID-19 modification, If MRI/MRI-PDFF assessment is not possible during the stated time period, due to COVID- restrictions, MRI/MRI-PDFF may be performed at a later timepoint, but prior to the last possible visit, which is on Day 113. If MRI/MRI-PDFF assessment is not possible due to restricted access of MRI center under COVID-19 restrictions, the missing assessment will be documented in the CRFs (specific information will be captured that explains the basis of the missing data due to COVID-19). The missing assessment will be documented as a protocol deviation (with reason due to COVID-19 stated).

③ Blood sample collection

- Incretins/metabolic hormones: Glucagon-like peptide-1 (GLP-1), gastric inhibitory polypeptide (GIP), glucagon, fibroblast growth factor 21 (FGF 21), leptin.
- Serum lipid profiles: Total cholesterol, low-density lipoprotein (LDL), high-density lipoprotein (HDL), very low-density lipoprotein (VLDL), triglycerides, free fatty acids (FFAs).
- Amino-acid profile

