WHO DDE	World health organization drug dictionary
WHR	Waist hip ratio

1. Introduction

This document describes the statistical methods and data presentation in the analysis and summary of the safety, tolerability, pharmacokinetics (PK) and pharmacodynamics (PD) of HM15136 in obese or overweight subjects with comorbidities. The original statistical analysis plan (SAP) was developed based on Hanmi Pharmaceutical Protocol HM-GCG-102 (version 5.0 dated 20 MAY 2020) and case report form version 5.0 dated 11 JUNE 2020 for Part 2 Study and 6.0 dated 6 JULY 2020 for Part 1 Study.

The original SAP was finalized prior to data analyses and before database lock of Part 1 Study. The current SAP amendment is created to incorporate contents from protocol version 6.0 (dated 29 OCTOBER 2020, post Part 1 database lock) regarding the change of time point for dose escalation from Cohort 5 to Cohort 6 and additional Data Review Meeting (DRM). The conduct of Cohorts 6 and 7 is determined to be optional for Part 2 Study.

Any major differences between the statistical methods provided in the clinical study protocol and this SAP will be explained herein. Any major changes and deviations from this SAP to the final data analysis must be substantiated by sound statistical rationale and fully documented in the final clinical study report (CSR).

2. Study Overview

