The dose of Cohorts 3 and 4 can be adjusted, but may not be over the planned dose of 0.08 mg/kg. The escalated dose should not be more than 2 times over the dose of the previous cohort.

In Part 2, after the review of the safety data, obtained by the 9th subject's visit on Day 29 of Cohort 3 (in Part 1), Cohort 4 can proceed with a dose of ≤ 0.08 mg/kg dose, which is the planned maximum dose.

A DMC will assess the safety and will make dosing and cohort escalation assessments and recommendations for the study progress of Part 2. After the review of the safety data in Part 1, Part 2 may or may not proceed. Cohort 4 may be conducted with a lower number of subjects. Cohort 5 may start immediately and may overlap with the conduct of subjects in Cohort 4.

In Part 2, dose escalation from Cohort 5 to the subsequent Cohort 6 will be made after a DRM, held by Sponsor, Investigator and Medical Monitor, and the safety data obtained from the 9th subject's visit on Day 43 (=after 6 weeks of dosing) will be reviewed. Per DRM of Cohort 5 (after the 9th subject's visit on day 43 of Cohorts 5), a dose escalation to Cohort 6 will not proceed and another DRM will be held after all 12 subjects in Cohort 5 have completed the final study visit on Day 113 (=F/U Visit), in order to assess the safety data.

Dose escalation from Cohort 6 to the subsequent Cohort 7 will follow the same dose escalation scheme and DRM(s) of the previous cohort.

Cohorts 6 and Cohort 7 may be conducted at doses of 0.04 mg/kg and at 0.06 mg/kg respectively upon approval by the Investigator, Medical Monitor, and the Sponsor, if the safety is demonstrated in Cohort 5. If sufficient safety data are collected after cohort 5 or cohort 6 have been completed, no additional cohorts will be conducted, and sponsor may choose to complete study.

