6.1. General Considerations

Summary and analysis of Part 1 and Part 2 will be separate. Placebo subjects within each part of the study will be pooled in summaries and listings. Exploratory analysis for subgroup of subjects being impacted by COVID-19, versus those not being impacted, may be conducted to assess missing data due to COVID-19. As the number of subjects in the subgroup analysis will be much smaller than the original planned population, caution should be taken when interpreting the inferential statistical results. Please refer to Sections 6.3 and 6.4 for COVID-19 subgroup analyses.

All data collected in the EDC and external data sets will be listed using the safety population.

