6.4.1. Analysis of Exploratory Incretins/Metabolic Hormone Endpoints

The observed values and the change from baseline in incretins/metabolic hormone endpoints, such as GLP-1, GIP, glucagon, FGF21 and leptin, will be summarized descriptively by cohort/dose level and time point.

A mixed model repeated measures analysis will be performed with the change from baseline in incretins/metabolic hormone endpoint as the dependent variable, treatment group, analysis visit and the interaction between treatment group and analysis visit as factors, and the baseline of the dependent variable as a covariate. Repeated measures on each subject, at each visit, will assume an unstructured covariance structure. If the model fails to converge, other covariance structures will be considered and selected based on model fit as determined by Akaike information criterion.

The least squares (LS) mean, standard error of LS mean and 95% confidence interval will be presented by treatment group for each post baseline analysis visit. The LS mean difference between active treatment group minus pooled placebo, standard error of the LS mean difference from placebo, and the 95% confidence interval will be presented by analysis visit.

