6.4.7. Analysis of Exploratory Anthropomorphic Measure Endpoints

The observed values and the change from baseline and percent change from baseline in anthropomorphic measures such as, body weight, BMI, waist circumference, hip circumference, WHR, will be summarized descriptively by cohort/dose level and time point.

A similar mixed model repeated measures analysis as described previously will be performed for the change from baseline and percent change from baseline in anthropomorphic measure endpoints.

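### Absolute change in visceral fat volume is compared with pooled placebo by an ANOVA without a baseline term; adding baseline is an optional, nearly free improvement for Part 2

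*SAP*

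**What the plan says.** SAP 6.4.6 gives liver fat (MRI-PDFF) and visceral fat volume two analyses of change and percent change from baseline. The first is a Wilcoxon Mann Whitney test with a Hodges-Lehmann estimate. The second is a parametric comparison: "an analysis of variance (ANOVA) model will be performed; the difference between each HM15136 dose group and placebo", with its 95% CI and p-value. No covariate is named there, and none is named for these endpoints elsewhere in the SAP.

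The model in SAP 6.4.1 has treatment, visit and their interaction, "and the baseline of the dependent variable as a covariate". Later sections reuse it for lipids, glucose parameters, HOMA, anthropometric measures, temperature, and inflammatory and ketone markers. SAP 6.4.7, for instance, states: "A similar mixed model repeated measures analysis as described previously will be performed".

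Protocol 10.2.2 (MRI imaging) sets the purpose of the scan: "The MRI imaging will be used to assess changes in visceral fat volume, determined by absolute and relative percent changes". On the pre-dose scan it says: "This test is performed prior to Day -1 for all eligible subjects".

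SAP 6.1 defines the comparator: "Placebo subjects within each part of the study will be pooled in summaries and listings". The two parts are analysed separately. On size, SAP 2.1 warns: "Cohort 4 may be conducted with a lower number of subjects". SAP 1 describes protocol version 6.0, which this SAP amendment incorporates, as "dated 29 OCTOBER 2020, post Part 1 database lock".

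**The concern.** Body weight, BMI and waist circumference are adjusted for their own baseline. Visceral fat volume is not, and no reason is given. It has one scheduled post-baseline scan, so the repeated-measures model does not apply directly; its single-visit counterpart is ANCOVA.

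The groups are small, so chance baseline differences from pooled placebo will be common. An unadjusted comparison of change passes part of such a difference into the estimated effect. If subjects with more visceral fat at the start tend to lose more, the group that starts higher looks better than it should. If the spread grows enough over time, the distortion reverses. What is at stake is the reported Part 2 difference and its interval for one exploratory endpoint. No dose decision depends on it.

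The point covers absolute change in visceral fat volume only. Nothing is claimed for liver fat, whose Day 85 scan is restricted to subjects with at least 10% at baseline, or for percent change.

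**Working it through.** The plan gives no power, SD or effect size for this endpoint, so there is no figure of its own to reproduce.

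**Inputs from the documents.** Part 2 allocation is 15:15 in Cohort 4 and 9:3 in each of Cohorts 5 to 7, and Cohorts 6 and 7 are optional (SAP 2.2, 2.3). Without them the groups are 15, 9 and pooled placebo 15 + 3 = 18, so N = 42 with g = 3 groups. Part 1 has four groups of 9 (N = 36). Intervals are 95% (SAP 6.4.6).

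**Assumed inputs.** Neither ρ (correlation of baseline with Day 85) nor k (Day 85 SD over baseline SD) is given, so ranges are shown. Early closure of Cohort 4 is illustrated by an assumed 6:6, giving groups of 6, 9 and 6 + 3 = 9.

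**1. CI width, ANCOVA over ANOVA**

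Expected ratio = √[k²(1 − ρ²) / (1 + k² − 2ρk)] × √[1 + 1/(N − g − 2)] × t(N − g − 1)/t(N − g)

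The first factor is the gain from removing baseline variation. The other two are the cost: random imbalance in the covariate and one residual degree of freedom.

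For N = 42 the cost is √(1 + 1/37) × 2.0244/2.0227 = 1.014. With k = 1 and ρ = 0.5 the gain factor is √0.75 = 0.866, and 0.866 × 1.014 = 0.878.

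| Groups | k | ρ = 0.5 | 0.7 | 0.8 | 0.9 |
|---|---|---|---|---|---|
| Part 2: 15, 9, 18 | 0.8 | 0.77 | 0.80 | 0.81 | 0.79 |
| | 1.0 | 0.88 | 0.94 | 0.96 | 0.99 |
| | 1.3 | 0.97 | 1.01 | 1.01 | 0.97 |
| Part 2: 6, 9, 9 (assumed) | 0.8 | 0.78 | 0.82 | 0.82 | 0.80 |
| | 1.0 | 0.89 | 0.95 | 0.98 | 1.00 |
| | 1.3 | 0.98 | 1.02 | 1.03 | 0.99 |
| Part 1: four groups of 9 | 0.8 | 0.77 | 0.81 | 0.82 | 0.79 |
| | 1.0 | 0.88 | 0.94 | 0.97 | 0.99 |
| | 1.3 | 0.97 | 1.01 | 1.02 | 0.98 |

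Simulation of 40,000 trials per setting agrees with the formula to within about 0.002.

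**2. Largest cost**

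This arises when ρk = 1, where change is unrelated to baseline. In simulation the expected interval is 1.4% wider with 15, 9, 18; 2.1% with 9, 9, 12; 2.8% with 6, 9, 9; 3.6% with 4, 9, 7; and 1.7% in Part 1. If all of Cohorts 4 to 7 run (N = 66), the formula gives 0.9%.

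**3. Chance imbalance, 15 against 18**

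In baseline SD units the standard error of the baseline difference is √(1/15 + 1/18) = 0.350. A difference beyond one standard error in either direction occurs in 32% of comparisons. Its mean size is then 0.350 × φ(1)/[1 − Φ(1)] = 0.350 × 1.525 = 0.53 SD. Unadjusted change carries the fraction (1 − ρk) of it:

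| k | ρ = 0.5 | 0.7 | 0.9 |
|---|---|---|---|
| 0.8 | 0.32 | 0.23 | 0.15 |
| 1.0 | 0.27 | 0.16 | 0.05 |
| 1.3 | 0.19 | 0.05 | −0.09 |

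Entries are the mean error in baseline SDs. A positive entry overstates the loss in the group that started higher; the negative entry understates it. In simulation the ANCOVA error is 0.00 to within about 0.005. With no true effect and k = 1, the nominal 5% ANOVA test rejects in about 9.2%, 7.6% and 5.8% of these imbalanced comparisons at ρ = 0.5, 0.7 and 0.9, against about 5% for ANCOVA. Over all comparisons the ANOVA rejects in about 5%, as it should.

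**The case against.** The strongest case is that nothing here is wrong. The ANOVA is valid, the endpoint is exploratory, and a rank-based analysis is reported beside it. That stands and sets the priority. The rank test uses the same unadjusted change, however, so it does not remove the imbalance.

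The gain may be nil. With k = 1 and ρ = 0.9, ANCOVA gives the narrower interval in only 52% of simulated trials at 15, 9, 18 and 39% at 6, 9, 9. This also stands: no percentage gain can be promised.

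The imbalance figures select the less balanced third of comparisons. With k = 1 the planned 95% half-width is 2.0227 × 0.350 × √[2(1 − ρ)] = 0.71, 0.55 and 0.32 SD at ρ = 0.5, 0.7 and 0.9. The mean errors of 0.27, 0.16 and 0.05 are thus 38%, 29% and 17% of it. They are just under half at k = 0.8. So the error normally lies inside an interval that already allows for chance imbalance. That is fair context, but it does not make the unadjusted estimate preferable.

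The COVID-19 visit lists in Protocol 10.2.1 make the pre-dose scan subject to availability and allow a late or missing follow-up scan, so the planned sizes are an upper limit. Against this, the footnote to the COVID-19 study flow requires the MRI before first dosing. A subject without a baseline scan has no change score under either model.

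Finally, adjusting only absolute change leaves percent change unadjusted, and the primary model would differ between Part 1 and Part 2. Both are true. The second follows from the Part 1 lock and is eased by showing the ANCOVA for Part 1 as supplementary.

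**Conclusion.** The point holds as an optional improvement, not an error. At planned Part 2 size, the effect of adding baseline runs from an expected interval about 23% narrower (k = 0.8, ρ = 0.5) to 1.4% wider (ρk = 1). With equal SDs the gain is about 12% at ρ = 0.5, 4% at 0.8 and 1% at 0.9. Adjustment also removes the baseline carry-over, which averages 0.05 to 0.27 SD in the less balanced third of comparisons (equal SDs, ρ from 0.9 down to 0.5).

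These figures assume bivariate normal values, a common linear slope, complete pairs of scans, and groups that differ at baseline only by chance. With placebo pooled across cohorts, the last of these also requires that the cohorts of a part draw on the same population. Most Part 2 placebo subjects would come from Cohort 4 (15 of 18 without Cohorts 6 and 7), and a baseline term does not replace a cohort term.

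**What to change.** In SAP 6.4.6, before Part 2 is unblinded, specify for absolute change in visceral fat volume an ANCOVA with treatment group as factor and baseline visceral fat volume as covariate. Report LS mean differences from pooled placebo with 95% CIs. For Part 1, already locked, present the same model as supplementary to the planned ANOVA. Keep the Wilcoxon/Hodges-Lehmann analysis, and leave the liver-fat and percent-change analyses as planned.

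The cost is one sentence, one residual degree of freedom and the common-slope assumption. No extra data are needed and no subject is dropped.

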6.4.7. Analysis of Exploratory Anthropomorphic Measure Endpoints

The observed values and the change from baseline and percent change from baseline in anthropomorphic measures such as, body weight, BMI, waist circumference, hip circumference, WHR, will be summarized descriptively by cohort/dose level and time point.

A similar mixed model repeated measures analysis as described previously will be performed for the change from baseline and percent change from baseline in anthropomorphic measure endpoints.

6.4.8. Analysis of Tympanic Temperature

The observed values and the change from baseline and percent change from baseline in tympanic temperature will be summarized descriptively by cohort/dose level and time point for 4AM, 6PM, and combined.

A similar mixed model repeated measures analysis as described previously will be performed for the change from baseline and percent change from baseline in tympanic temperature for 4AM, 6PM, and combined.

6.4.9. Analysis of Exploratory Inflammatory Markers and Ketone Body Endpoints

The observed values and the change from baseline in inflammatory markers, such as hs-CRP and adiponectin, and the observed values and the change from baseline in ketone bodies such as β -hydroxybutyrate, will be summarized descriptively by cohort/dose level and time point.

A similar mixed model repeated measures analysis as described previously will be performed for the change from baseline in inflammatory markers and ketone body endpoints.

7. Interim Analysis

An interim analysis will be performed for administrative purposes, to aid in the planning of future studies in the development program after all healthy subjects in Part 1 have been finalized. Part 1 includes all subjects in Cohorts 1-3. As COVID-19 may lead to challenges in the collection of data, only partially validated data might be available for the planned interim analysis. This interim analysis will be performed for administrative purpose prior to database lock of Part 1. Unblinding will occur prior to the database lock for Part 1. Designated personnel not involved in the study conduct will perform the above stated interim analysis. Only authorized members who are listed in the Interim Analysis Unblinding and Information Dissemination Plan will have access to review the summary tables or figures of the interim analysis results, in which the information is presented in a grouped fashion with the actual treatment, e.g., mean treatment effect. The interim analysis will include an assessment of all efficacy, safety, and PK variables of Part 1.

HM-GCG-102 Statistical Analysis Plan

An additional interim analysis will be performed after database lock for Part 1, which is the final analysis of Part 1. The final analysis results of part 1 will be included in the final CSR along with the final analysis of Part 2.

Both analyses for Part 1 may occur, while Part 2 will continue in a blinded fashion. The study will be conducted as outlined in this protocol. Part 2 will be performed independently from the conduct/results of the Part 1 and will not lead to changes to the conduct of the protocol. After Part 2 (T2DM cohorts) has been completed, a final analysis, that only includes the results of Part 2, will be conducted after data base lock of Part 2. For details on the interim analysis based on semi-clean data, please refer to the Interim Analysis Unblinding and Information Dissemination Plan.

8. Statistical Software

All statistical analyses will be performed using SAS® version 9.4. PD parameters will be derived with SAS® version 9.4. PK parameters will be derived with standard non-compartmental methods using WinNonlin v5.2 or higher.

9. References

10. Appendix

10. Appendix

Table 2: Schedule of Events

Schedule of Events (Part 1)

HM-GCG-102 Statistical Analysis Plan

Assessment	V1	V2	V3-15										V16	V17-19	
			OPD												
Visit(Week)	-5 to -1		1	2	2	3	4	5	6	7	8	9	10	11	13
Visit(day)	-35 to -3	-2	-1	1	2	3	4	5	6-7	8	10	11	15	17	15
Visit window															17
Sequestered in clinic/unit	X	X	X	X	X	X	X	X	X	X	X	X	X	X	99
Physical examination	X														113
Abbreviated Physical examination	X														
Vital sign ²	X	X	X	X	X	X	X	X	X	X	X	X	X	X	X
12-lead ECG ³	X	X	X	X	X	X	X	X	X	X	X	X	X	X	X
ABP monitoring ⁴	X	X	X	X	X	X	X	X	X	X	X	X	X	X	X
Holter monitoring ⁴		X	X	X	X	X	X	X	X	X	X	X	X	X	X
Clinical laboratory test (Hematological, Chemistry ⁵ , Blood coagulation, Urine analysis)	X	X	X ⁶	X	X	X	X	X	X	X	X	X	X	X	X
Other Safety assessment															
Concomitant medications	X	X	X	X	X	X	X	X	X	X	X	X	X	X	X
Adverse events	X	X	X	X	X	X	X	X	X	X	X	X	X	X	X
Injection site reactions			X	X	X	X	X	X	X	X	X	X	X	X	X
Pharmacodynamics (PD) assessment ⁶															
MRI/MRI-PPF ⁷			X ⁸												X ⁹
Body weight, BMI	X	X	X												X
Height	X														X
Tympanic temperature (2x/day) ¹⁰		X	X	X	X	X	X	X	X	X	X	X	X	X	X

HM-GCG-102 Statistical Analysis Plan

Assessment	V 1		V 2		V 3-15										V 16		V 17-19															
	Screening		In-house Period 1		OPD										In-house Period 2		OPD (F/U)															
Visit(Week)	-5 to -1		1	2	3	4	5	6	7	8	9	10	11	12	13	15	17															
Visit(day)	-35 to -3	-2	-1	1	2	3	4	5	6-7	8	10	11	15	17	18	22	29	36	43	50	57	64	71	77	78	79	80	81	82	85	99	113
Visit window											+1		+2	+2	+2	+2	+2	+2	+2	+2	+2	+2	+2	+2								
Sequestered in clinic/unit																																
Waist circumference, Hip circumference, Waist-to-hip ratio (WHR)																																
7-point Self-monitoring of blood glucose (SMBG) ⁶																																
Glucose measure (via YSI) ¹¹																																
HbA1c																																
Fructosamine, glycated albumin																																
Fasting plasma glucose (FPG)																																
Fasting insulin, Fasting C-peptide																																
HOMA-IR, HOMA- β																																
Incretins / metabolic hormones																																
Amino-acid profile																																
Serum lipid profiles																																
Inflammatory markers																																
β -hydroxybutyrate																																

HM-GCG-102 Statistical Analysis Plan

Assessment	V1		V2		V3-15					V16			V17-19							
	Screening		In-house Period 1					OPD					In-house Period 2			OPD (F/U)				
Visit(Week)	-5 to -1		1	2	2	3	4	5	6	7	8	9	10	11	11	12	13	15	17	
Visit(day)	-35 to -3	-2	-1	1	2	3	4	5	6-7	8	10	11	15	17	18	22	29	43	50	57
Visit window																±2	±2	±2	±2	±2
Sequestered in clinic/unit																				
pharmacokinetic (PK), immunogenicity assessment																				
Immunogenicity (ADaps, nAbs, anti-PEG)																				
PK assessment ^a																				

1 Only that are eligible for in-house period and past medications (stated as #1-5 in section 10.1.1-3) in-house period.

2 Sampling for PK assessment and YSI to be measured on the day should be conducted before each PK sampling (prior to the collection of Pre-dose Samples on Day 1 and Day 78).

3 At the screening visit, a 12-lead ECG is conducted 1 time. All other 12-lead ECGs should be repeated 3 times. Additional measurements of the 12-lead ECG may be conducted during the following specified in-house period, which is also repeated 3 times.

The ECG measurements are collected on Day -2 and Day 77 before the subject is connected to the ABP monitoring device and on the Day 5 and Day 82 after the subject is disconnected to the ABP monitoring device.

4 Measurement time point may be adjusted after PK assessment.

5 Serum ferritin in the chemistry laboratory test is measured on the Day 1 before the administration, Day 57, Day 85.

6 All PD assessment endpoints are collected at the same time on fasting conditions at the time of PK Sample collection (Pre-dose Sample collection on Day 1 and Day 78). In the case of fasting conditions, the test subject should be kept in a state of being maintained for about 10 hours.

7 MRI/MRI-PDF assessment marked for Day -1 can be performed prior to Day -1, after subject's eligibility for the study is confirmed (MRI may be performed while Screening calcitonin results are pending). MRI-PDF measurements marked for Day 85 should be conducted as close as possible to the Day 85 of the 12th week before the Day 85 PK sampling, and on Day 85 of the MRI-PDF measurement, the MRI-PDF will only be performed if the MRI-PDF on Day -1 showed equal or more than 10% liver fat. MRI assessment will be performed as close as possible to the Day 85 of the 12th week before the Day 85 PK sampling.

8 The 7-point SMBG is measured 15 minutes before the meal (\pm 10 minutes), 2 hours after the meal starts (\pm 15 minutes), and 15 minutes before the evening snack (\pm 10 minutes). For the Day 1 and Day 78 of the test, 5 times, except before and after breakfast, should be conducted.

9 The time of PK sampling may be adjusted between cohorts if PK data showing that other time points are more advantageous can be obtained when the sample for pharmacokinetic analysis is collected. Specific PK sampling timeline for analysis follows the PK sampling schedule table.

10 During the in-house periods, tympanic temperature will be measured 2 x/24 hours.

11 FPG will be measured via YSI in addition to the FPG measure that is included in clinical laboratory assessments. The measurement of glucose via YSI should be performed for all subjects and for all outpatient visits.

Schedule of Events (Part 2)

HM-GCG-102 Statistical Analysis Plan

Assessment	V1		V2		V3-15										V16		V17-19																	
	Screening		In-house Period 1		OPD										In-house Period 2		OPD (F/U)																	
Visit(Week)	-5 to -1		1	2	2	3	4	5	6	7	8	9	10	11	11	12	13	15	17															
Visit(day)	-35 to -3	-2	-1	1	2	3	4	5	6-7	8	10	11	15	17	18	22	29	36	43	50	57	64	71	77	78	79	80	81	82	85	99	113		
Visit window																																		
Sequestered in clinic/unit																																		
LH, FSH (Only female)																																		
Physical examination	X																																	
Abbreviated Physical examination	X																																	
Vital sign ²	X	X	X	X	X	X	X	X	X	X	X	X	X	X	X	X	X	X	X	X	X	X	X	X	X	X	X	X	X					
12-lead ECG ³	X	X	X	X	X	X	X	X	X	X	X	X	X	X	X	X	X	X	X	X	X	X	X	X	X	X	X	X	X					
ABP monitoring ⁴	X	X	X	X	X	X	X	X	X	X	X	X	X	X	X	X	X	X	X	X	X	X	X	X	X	X	X	X	X					
Holter monitoring ⁴																																		
Clinical laboratory test (Hematological, Chemistry ⁵ , Blood coagulation, Urine analysis)																																		
Other Safety assessment																																		
Concomitant medications	X	X	X	X	X	X	X	X	X	X	X	X	X	X	X	X	X	X	X	X	X	X	X	X	X	X	X	X						
Adverse events	X	X	X	X	X	X	X	X	X	X	X	X	X	X	X	X	X	X	X	X	X	X	X	X	X	X	X	X						
Injection site reactions																																		
Pharmacodynamics (PD) assessment ⁶																																		
MR/MRI+DFF ⁷																																	X ⁷	
Body weight, BMI	X	X	X	X	X	X	X	X	X	X	X	X	X	X	X	X	X	X	X	X	X	X	X	X	X	X	X	X	X					
Height	X																																	
Tympanic temperature (2x/day) ¹⁰																																		

HM-GCG-102 Statistical Analysis Plan

Assessment	V1	V2	OPD										V16	V17-19	
			In-house Period 1			V3-15			In-house Period 2						
Visit(Week)	-5-to -1		1	2	2	3	4	5	6	7	8	9	10	11	12
Visit(day)	-35 to -3	-2	-1	1	2	3	4	5	6-7	8	10	11	15	17	18
Visit window															
Sequestered in clinic/unit	X	X	X	X	X	X	X	X							
Waist circumference, Hip circumference, Waist-to-hip ratio (WHR)	X	X	X				X				X	X	X	X	X
7-point Self-monitoring of blood glucose (SMBG) ⁸			X	X	X	X									
Glucose measure (via YS) ¹¹							X	X	X	X	X	X	X	X	X
HbA1c	X	X													X
Fructosamine, glycated albumin			X												X
Fasting plasma glucose (FPG)	X	X	X	X	X	X	X	X	X	X	X	X	X	X	X
Fasting insulin, Fasting C-peptide	X		X	X	X	X	X	X	X	X	X	X	X	X	X
HOMA-IR, HOMA- β		X													X
Incretins / metabolic hormones		X	X			X			X			X		X	X
Amino-acid profile		X	X			X			X			X		X	X
Serum lipid profiles	X		X			X			X			X		X	X
Inflammatory markers		X	X			X			X			X		X	X
β -hydroxybutyrate		X	X			X			X			X		X	X

HM-GCG-102 Statistical Analysis Plan

Assessment	V1		V2		V3-15					V16		V17-19							
	Screening		In-house Period 1					OPD					In-house Period 2						
Visit(Week)	-5 to -1		1	2	2	3	4	5	6	7	8	9	10	11	12	13	15	17	
Visit(day)	-35 to -3	-2	-1	1	2	3	4	5	6-7	8	10	11	15	17	18	22	29	36	43
Visit window																			
Sequestered in clinic/unit																			
Pharmacokinetic (PK) immunogenicity assessment																			
Immunogenicity (ADAs, nADs, anti-PEG)																			
PK assessment ^a																			

1 Only that are eligible for in-house period and past medications (stated as #1-5 in section 10.1.1-3) in-house period.

2 Sampling for PK assessment and V/S to be measured on the day should be conducted before each PK sampling (prior to the collection of Pre-dose Samples on Day 1 and Day 78).

3 At the screening visit, a 12-lead ECG is conducted 1 time. All other 12-lead ECGs should be repeated 3 times. Additional measurements of the 12-lead ECG may be conducted during the following specified in-house period, which is also repeated 3 times.

The ECG measurements are collected on Day -2 and Day 77 before the subject is connected to the ABP monitoring device and on the Day 5 and Day 82 after the subject is disconnected to the ABP monitoring device.

4 Measurement time point may be adjusted after PK assessment.

5 Serum ferritin in the laboratory test is measured on the Day 1 before the administration, Day 57, Day 95.

6 All PK assessment endpoints are collected at the same time on fasting conditions at the time of PK Sample collection (Pre-dose Sample collection on Day 1 and Day 78). In the case of fasting conditions, the test subject should be kept in a state of being maintained for about 10 hours.

7 MRI/MRI-PDF assessment marked for Day -1 can be performed prior to Day -1, after subject's eligibility for the study is confirmed (MRI may be performed while Screening calcitonin results are pending). MRI-PDF measurements marked for Day 85 should be conducted as close as possible to the Day 85 of the 12th week before the Day 85 PK sampling, and on Day 85 of the MRI-PDF measurement, the MRI-PDF will only be performed if the MRI-PDF on Day -1 showed equal or more than 1.0% liver fat. MRI assessment will be performed as close as possible to the Day 85 of the 12th week before the Day 85 PK sampling.

8 The 7-point SMBG is measured 15 minutes before the meal (\pm 10 minutes), 2 hours after the meal starts (\pm 15 minutes), and 15 minutes before the 15 minutes before the evening snack (\pm 10 minutes). For the Day 1 and Day 78 of the test, 5 times, except before and after breakfast, should be conducted.

9 The time of PK sampling may be adjusted between cohorts if PK data showing that other time points are more advantageous can be obtained when the sample for pharmacokinetic analysis is collected. Specific PK sampling timeline for analysis follows the PK sampling schedule table.

10 During the in-house periods, tympanic temperature will be measured 2 x/24 hours.

11 FPG will be measured via YSI in addition to the FPG measure that is included in clinical laboratory assessments. The measurement of glucose via YSI should be performed for all subjects and for all outpatient visits.

Schedule of Events (Part 1 and Part 2 COVID-19 Modification)

Assessment	V1	V2		V3-15										V16				V17-19					
		OPD		OPD										OPD				OPD (FU)					
Visit(Week)	-5 to -1			1	2	2	2	3	3	4	5	6	7	8	9	10	11	11	12	13	15	17	
Phone visit (P) (assessments at home) ¹¹		P	P	P	P	P	P											P	P	P			
Visit(day)	-35 to -3	-2 ¹¹	-1 ¹¹	1	2 ¹¹	3 ¹¹	4 ¹¹	5 ¹¹	6 ¹¹	7 ¹¹	8	10	11 ¹¹	15	17	18 ¹¹	22	29	36	43	50	57	64
Visit window		±1	±2	±1	±1	±1	±1	±1	±1	±1	±1	±1	±1	±1	±1	±2	±2	±2	±2	±1	±1	±2	±2
Administration IP			X							X		X		X		X		X		X			
Randomization		X																					
Procedure of Screening																							
Informed consent process	X																						
In/Exclusion criteria	X	X ¹																					
Demographics	X																						
Prior medication and medical history taking	X																						
Infection of HBV, HCV and Anti-body, infection of HIV	X																						
Pregnancy test (Urine)	X	X																					X
Serum FSH (Only Postmenopausal female)	X																						
eGFR	X																						
Drug abuse urine screening and alcohol exhalation test	X	X	X	X	X	X	X	X	X	X	X	X	X	X	X	X	X	X	X	X	X	X	X
Dietary education	X	X	X	X	X	X	X	X	X	X	X	X	X	X	X	X	X	X	X	X	X	X	X
Diet diary distribution	X	X	X	X	X	X	X	X	X	X	X	X	X	X	X	X	X	X	X	X	X	X	X
Diet diary review		X	X	X	X	X	X	X	X	X	X	X	X	X	X	X	X	X	X	X	X	X	X
Safety assessment																							
TSH	X	X																X			X	X	
Amylase, Lipase	X	X																X			X	X	
Calcitonin	X	X																X			X	X	

HM-GCG-102 Statistical Analysis Plan

Assessment	V1	V2	V3-15												V16			V17-19																					
			OPD			OPD			OPD			OPD			OPD			OPD (FU)																					
Visit(Week)	-5 to -1		1	2	2	3	4	5	6	7	8	9	10	11	12	13	15	17																					
Phone visit (P) (assessments at home) ¹¹		P	P	P	P										P	P																							
Visit(day)	-3 ¹¹	-1 ¹¹	1	2 ¹¹	3 ¹¹	4 ¹¹	5 ¹¹	6 ¹¹	7 ¹¹	8	10	11 ¹¹	15	17	18 ¹¹	22	29	36	43	50	57	64	71	77 ¹¹	78	79 ¹¹	80 ¹¹	81 ¹¹	82 ¹¹	85	90	99	11	3					
Visit window		t1	t2		t1	t1	t1	t1	t1	t2	t1	t2	t1	t2	t2	t2	t1	t1	t1	t1	t2	t2	t2	t2	t2	t2	t2	t2	t2	t2									
LH, FSH (Only female)			X								X				X																								
Physical examination	X																																						
Abbreviated Physical examination	X														X																								
Vital sign ²	X	X	X	X	X	X	X	X	X	X	X	X	X	X	X	X	X	X	X	X	X	X	X	X	X	X	X	X	X	X	X	X	X						
12-lead ECG ³	X														X	X	X	X	X	X	X	X	X	X	X	X	X	X	X	X	X	X	X	X					
ABP monitoring ⁴	X	X	X	X	X	X	X	X	X	X	X	X	X	X	X	X	X	X	X	X	X	X	X	X	X	X	X	X	X	X	X	X	X						
Instructions on ABPM at home	X																																						
Holter monitoring ⁴	X	X	X	X	X	X	X	X	X	X	X	X	X	X	X	X	X	X	X	X	X	X	X	X	X	X	X	X	X	X	X	X	X	X					
Instructions on Holter monitoring at home		X																																					
Clinical laboratory test (Hematological, Chemistry ⁵ , Blood coagulation, Urine analysis)	X														X	X	X	X	X	X	X	X	X	X	X	X	X	X	X	X	X	X	X	X	X				
Other Safety assessment																																							
Concomitant medications	X	X	X	X	X	X	X	X	X	X	X	X	X	X	X	X	X	X	X	X	X	X	X	X	X	X	X	X	X	X	X	X	X	X					
Adverse events	X	X	X	X	X	X	X	X	X	X	X	X	X	X	X	X	X	X	X	X	X	X	X	X	X	X	X	X	X	X	X	X	X	X					
Injection site reactions															X	X	X	X	X	X	X	X	X	X	X	X	X	X	X	X	X	X	X	X	X				
Pharmacodynamics (PD) assessment ⁶																																							
MRI/MRI-DFE ⁷			X ⁷																																				
Body weight, BMI	X	X	X												X	X	X	X	X	X	X	X	X	X	X	X	X	X	X	X	X	X	X	X	X				
Height	X																																						

HM-GCG-102 Statistical Analysis Plan

Assessment	V1	V2		V3-15										V16		V17-19																
		Screening		OPD		OPD										OPD		OPD		OPD		OPD/F/U										
Visit(Week)	-5 to -1	1		2		3		4		5		6		7		8		9		10		11		12		13		15				
Phone visit (P) (assessments at home) ¹¹		P	P	P	P	P	P																P	P	P	P						
Visit(day)	-35 to -3	-2 ¹¹	-1 ¹¹	1	2 ¹¹	3 ¹¹	4 ¹¹	5 ¹¹	6 ¹¹	7 ¹¹	8	10	11 ¹¹	15	17	18 ¹¹	22	29	36	43	50	57	64	71	77 ¹¹	78	79 ¹¹	80 ¹¹	81 ¹¹	82 ¹¹	85	99
Visit window		+1	+2		+1	+1	+1	+1	+1	+1	+1	+1	+1	+1	+1	+2	+2	+2	+2	+2	+2	+2	+1	+1	+1	+1	+1	+2	+2			
Waist circumference, Hip circumference, Waist-to-hip ratio (WHR)	X	X	X										X			X			X			X			X	X	X	X				
7-point Self-monitoring of blood glucose (SMBG) ¹²		X	X	X	X	X	X																		X	X	X	X				
Instructions on 7-point SMBG and FPG at home		X																							X							
SMBG and fasting blood glucose (FPG) diary distribution		X	X		X								X	X	X	X	X	X	X	X	X	X	X	X	X	X	X	X				
Glucose measure (via YSI) ^{10,12}	X	X	X	X								X	X	X	X	X	X	X	X	X	X	X	X	X	X	X	X					
HbA1c	X	X																														
Fructosamine, glycated albumin			X																													
